It is now clear that immunosuppressive strategies for renal transplantation achieve excellent short-term and medium-term results. Unfortunately, the long-term results have not substantially improved in the last 20 years. The reasons for this failure to achieve better long-term results are complicated and include such things as allowing older and sicker people to be recipients, using poorer quality donor kidneys and the complications associated with long-term immunosuppression. Among the worst of the long-term effects of chronic immunosuppression are the nephrotoxicity of the calcineurin inhibitors and the myriad complications of steroids. The goal of many now in the transplant field is to limit the exposure of transplant recipients to both steroids and calcineurin inhibitors. The following protocol evaluates the reduction of calcineurin inhibitors in a protocol that has already successfully eliminated the long-term use of steroids. Given the substantial experience with Campath® detailed above, the following study protocol will be offered to all patients undergoing renal transplantation at the University of Toledo University Medical Center. This is a small pilot study; multiple comparisons will be made for descriptive purposes only.

Hypothesis:

Our hypothesis is that conversion to everolimus (Zortress®), allowing the reduction of calcineurin inhibitors, will reduce nephrotoxicity (measured by increased creatinine clearance) and lengthen overall graft survival (measured by 2-year graft survival).

Objectives:

1. The primary objective of the study is to compare the efficacy and the effects on renal function of calcineurin-inhibitor reduction with conversion at 2 months after transplantation to Reduced Dose tacrolimus/everolimus in adult renal transplant recipients. Efficacy will be defined using two co-primary endpoints.
 - a. A composite efficacy end point [treated biopsy-proven rejection (BPAR), graft loss, death or loss to follow-up].
 - b. Renal function at 24 months post transplantation using GFR as measured by the Modified Diet Renal Disease (MDRD) estimation.

2. Secondary objectives will be to:
 - a. Compare the safety and tolerability of the experimental arm compared to the historical control arm.
 - b. Compare the presence of proteinuria as defined by spot urine protein to creatinine ratio greater than 1.0 in the experimental arm to the historical control arm.

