 - c. Compare the presence of hyperlipidemia in the experimental arm to the historical control arm.
 - d. Compare the incidence of impaired glucose tolerance (IGT) as assessed by fasting blood sugar, HbA1c and need for hypoglycemic medications in the experimental arm to the historical control arm.
 - e. Compare the incidence of mouth ulcers in the experimental arm to the historical control arm.
 - f. Compare the incidence of GI complaints including diarrhea in the experimental arm to the historical control arm.
 - g. Compare the incidence of leukopenia as defined by WBC less than 1.0, absolute neutrophil count less than 500 or the need for exogenous granulocyte stimulating factor administration in the experimental arm to the historical control arm.
 - h. Compare the incidence of thrombocytopenia at one year as defined by platelet count less than 50 or need to discontinue one of the study medications for more than 30 days in the experimental arm to the historical control arm.
 - i. Compare the incidence of neurotoxicity as defined by incidence of new onset seizure activity or tremors in the experimental arm to the historical control arm.
 - j. Compare the incidence of pneumonitis in the experimental arm to the historical control arm.
 - k. Compare the incidence of serious infections as defined by need for hospitalization in the experimental arm to the historical control arm.
 - l. Compare the incidence of CMV infection as defined by need for hospitalization in the experimental arm to the historical control arm.
 - m. Compare the incidence of BK infection as defined by blood titers requiring reduction in immunosuppressive dose in the experimental arm to the historical control arm.

n. Compare the incidence of BK nephropathy as defined by biopsy in the experimental arm to the historical control arm. Note that biopsies will not be required as part of the study but will only be done as part of the patient's standard of care if rejection is suspected (i.e. if the serum creatinine increases by 25% and is not associated with elevated tacrolimus levels or clinical signs of dehydration/illness to account for elevated creatinine).

o. Compare the incidence of malignancies including PTLN in the experimental arm to the historical control arm.

p. Compare the incidence of cardiovascular complications such as dysrhythmias, coronary artery disease requiring intervention or myocardial infarction in the experimental arm to the historical control arm.

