 - Adequate barrier methods of contraception include: diaphragm, condom (by the partner), intrauterine device (copper or hormonal), sponge or spermicide. Hormonal contraceptives include any marketed contraceptive agent that includes an estrogen and/or a progestational agent. Acceptable contraception methods will be discussed with all women of child-bearing potential.

- Reliable contraception should be maintained throughout the study and for 8 weeks after study drug discontinuation. For women who become pregnant while using Myfortic® or within 8 weeks of discontinuing therapy, we will report the pregnancy to the Mycophenolate Pregnancy Reference Registry ([name]) and will strongly encourage the patient to enroll in the pregnancy registry.
- Women are considered post-menopausal and not of child bearing potential if they have had 12 months of natural (spontaneous) amenorrhea with an appropriate clinical profile (e.g. age appropriate, history of vasomotor symptoms) or six months of spontaneous amenorrhea with serum FSH levels > 40 mIU/mL and estradiol < 20 pg/mL] or have had surgical bilateral oophorectomy (with or without hysterectomy) at least six weeks ago. In the case of oophorectomy alone, only when the reproductive status of the woman has been confirmed by follow up hormone level assessment is she considered not of child bearing potential.

Study Duration:

We plan to enroll 11 patients per year. Given this assumption, the enrollment will take five years. Adding two years of follow-up care, we will be able to complete the study in 7 years.

Study Design:

1. Single center pilot study utilizing historical control
2. A single treatment arm
3. Eleven patients per year
4. Five years to enroll 55 patients.
5. Enroll all patients who meet the inclusion criteria at 2 months and up to 6 months (± 10 days) post kidney transplantation and are willing to consent for this trial.
6. Patients would have study visits, serum creatinine measurements and other clinically relevant parameters measured monthly until 6 months, then q3 months until 2 years post-transplantation.
7. Graft survival would be measured by the absence of the need for dialysis.
8. It would not be mandatory, but a renal biopsy would be recommended at 2 years to look for underlying early signs of calcineurin toxicity/chronic allograft nephropathy.

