9. Secondary endpoints would include such parameters as post-transplant diabetes, proteinuria, lipid levels, mouth sores, neurotoxicity, pneumonitis, CMV, PTLN, BK-nephropathy, malignancies, cardiovascular complications, etc.
10. Our historical control will be composed of patients transplanted at the University of Toledo Medical Center between October 2011 and the beginning of this trial. All of those patients will have been treated with the exact same protocol as in this study except that they will not have been converted to the treatment arm above, but will have remained on tacrolimus and myfortic®, unless the clinical situation warranted changing immunosuppression. We expect that the control group will consist of approximately 50-55 patients and will have similar demographics to the patients that will be enrolled in this trial, given that we will use the same inclusion and exclusion criteria to select all patients from October 2011 until the start of this trial to populate

the historical control group. The reason for October 2011 as the starting point for the historical control is that this is the date when we modified our protocol to add a five day taper of steroids immediately after transplantation. Prior to that we only gave steroids immediately prior to the transplantation procedure. Thus, to be consistent with the patients in this trial, we believe the most accurate historical control should have the same treatment with steroids perioperatively. We will utilize all patients available in the historical control dataset and will not attempt to match for the demographics present in the experimental arm. The control group will consist of a historical control; prospective patients who are not willing to participate in the study will not be considered part of the control group.

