 18. For patients with elevated, post-transplant creatinine but without biopsy proven evidence of cellular or humoral rejection, causes of elevated creatinine other than rejection should be considered. These include intercurrent illness, dehydration, BK-nephropathy and tacrolimus toxicity. Dose reduction of tacrolimus can be attempted to assess for the possibility of calcineurin-inhibitor nephrotoxicity. If dose reduction of tacrolimus is not acceptable, then everolimus (first choice) or Neoral® (second choice) will be used as replacement therapy.
 19. Upon discharge from the hospital, all patients will be treated with the following prophylactic medications:
 - a. Valcyte® 450 mg PO daily to prevent subsequent CMV infection (unless leukopenia or other side effects warrant further dose reduction or discontinuation). Valcyte® will be administered for 6 months if there is no CMV mismatch and for 12 months if there is a CMV mismatch.
 - b. Bactrim DS® one tablet PO Monday, Wednesday and Friday to prevent subsequent pneumocystis carinii pneumonia. In hospital desensitization with [name] can be performed if the patient has a known sulfa allergy or Dapsone replacement can be used. Bactrim® will be administered for at least one year following transplantation. Length of therapy after one year will be determined by physician and patient preference.
 - c. Mycelex® Troche one lozenge PO QID to prevent oral thrush. Mycelex troche® therapy will be continued for 6 months post-transplantation.
 - d. Flagyl® 500 mg PO TID to prevent Clostridium difficile infection only during in-hospital stays of transplant patients.
 20. BK viral titers will be assessed at three month intervals for the first year post-operatively.
 21. Post-transplant PRAs (to determine the presence or absence of donor specific antibodies – DSA) will be assessed at the patient's screening visit, at three month intervals for the first year post-operatively and every 6 months in the

second year post-operatively. PRAs may also be assessed at the discretion of the principal investigator or measured as part of the patient's standard of care/routine treatment.

22. For patients who are prescribed myfortic® as part of an intention-to-treat adverse event, MPA levels will be assessed on an as needed basis.

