This will be a small, pilot study to test whether conversion to everolimus (Zortress®), allowing the reduction of calcineurin inhibitors, will reduce nephrotoxicity (measured by increased creatinine clearance) and lengthen overall graft survival (measured by 2-3 year graft survival). As it is not a large study (55 patients, 11 patients per year), it is not powered to achieve statistical significance. The statistical significance will also be impaired by the use of a historical control group. However, the data generated will be published irrespective of the results, thus making the data available for meta-analysis.

This trial is designed as a parallel-group study. Analysis of data for this design is simple and interpretation of the result is straightforward. Given the limited number of

patients in the trial it may not be meaningful to apply analysis of (co)variance for the statistical evaluation of a continuous variables such as creatinine clearance, but we will attempt to use this method with the guidance of our statistician, [name].^{19,20} Likewise, the limited number of patients in the trial may prevent meaningful analysis of time-to-event variables such as graft survival. Nonetheless, we will work with [name] to use methods appropriate for survival analysis including the Kaplan-Meier method and Cox's proportional hazards regression to see if meaningful differences exist between our study groups and our historical control.^{21,22} If warranted, for safety analyses the AEs and SAEs could be summarized by treatment group but no statistical tests performed due to the population size as a pilot study. In addition, the PI and Co-PI will meet with other members of the clinical transplant team to review the results of this study on a quarterly basis to ensure that no significant adverse events warrant the discontinuation of the trial. Given the small number of patients in the trial, we will analyze the data after we have enrolled 10 patients. If the study immunosuppression regimen has a > 40% Banff 2a rejection rate or greater than 20% patient death rate, then that arm will be prematurely terminated. Serious adverse events will also be analyzed and may serve as grounds for study discontinuation.

Everolimus IIRP Pilot Study Evaluation and Visit Schedule

Treatment Period															
			Months												
	Screening (Visit 1)	Baseline (Visit 2)	1 (3)	2 (4)	3 (5)	4 (6)	5 (7)	6 (8)	9 (9)	12 (10)	15 (11)	18 (12)	21 (13)	24 (14)	

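### BK infection (objective 2m) has no time window, and scheduled titres run into year 2 for trial patients but apparently not for the historical controls

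*Combined protocol and SAP*

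**What the plan says.** Objective 2m concerns the "incidence of BK infection as defined by blood titers requiring reduction in immunosuppressive dose", experimental arm against historical control. No interval is stated for it.

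Two places give timed BK testing:

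- **Evaluation and Visit Schedule (trial patients):** titres at months 1, 3, 6, 9, 12, 18 and 24.
- **Detailed Renal Transplantation Immunosuppression and Management Protocol, item 20:** "BK viral titers will be assessed at three month intervals for the first year post-operatively". Nothing is scheduled for year 2.

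Item 23 of the same protocol adds BK testing without set times when a raised creatinine suggests rejection.

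The design has "A single treatment arm", so the comparator is the historical control. Study Design item 10 says of those controls: "All of those patients will have been treated with the exact same protocol as in this study", apart from the conversion. It adds "We will utilize all patients available in the historical control dataset", without describing what monitoring or safety data that dataset holds.

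For BK nephropathy (2n), the Objectives limit biopsies to suspected rejection. Study Design item 8, however, says "a renal biopsy would be recommended at 2 years", although it is not mandatory.

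On adverse events generally, objective 2a is to "Compare the safety and tolerability of the experimental arm compared to the historical control arm". For the overall adverse-event summary, the Statistical Section offers only this: "If warranted, for safety analyses the AEs and SAEs could be summarized by treatment group but no statistical tests performed due to the population size".

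**The concern.** An endpoint defined by a blood titre can be met only if a titre is taken. If one group is screened in year 2 and the other is tested only when creatinine rises, the first will show more infections at the same true incidence. The comparison could then report a BK excess on everolimus that comes from testing, or mask a true reduction. Small numbers do not excuse this. It is a bias rather than imprecision, it affects a purely descriptive difference, and the Statistical Section intends the data for meta-analysis, where the bias would be carried forward.

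2n has a related problem: a 2-year biopsy done on recommendation could find nephropathy in a patient who would not otherwise have had a biopsy.

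**Working it through.** The plan states no BK rate, so there is no figure to reproduce. The check counts scheduled titres, then asks how much the difference could matter.

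**1. Which clock.** Study Design item 6 describes visits up to two years post-transplant. The visit table instead puts screening (at 2 to 6 months) and baseline before month 1. Both readings are used, with entry at month 2.

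| Reading | Trial titres, months after transplant | Item 20 | Up to month 12 | Months 12 to 24 |
|---|---|---|---|---|
| From transplant | 3, 6, 9, 12, 18, 24 (month 1 precedes entry) | 3, 6, 9, 12 | 4 v 4 | 2 v none scheduled |
| From baseline | 3, 5, 8, 11, 14, 20, 26 | 3, 6, 9, 12 | 4 v 4 | 2 v none scheduled (one more trial titre at 26) |

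Entry at month 6 on the baseline reading gives titres at 7, 9, 12, 15, 18, 24 and 30: 3 v 2 from conversion to month 12, and 3 v none scheduled in year 2. The firm difference is in year 2.

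**2. Share of episodes caught.** Assume a case counts if a scheduled titre falls within *d* months after onset, and that incidence refers to episodes that would prompt a dose reduction if found. Creatinine-prompted tests are ignored. The share caught is the proportion of onsets followed by a titre within *d*. Take *d* = 3.

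*Even onset, transplant reading (22 months, 2 to 24).* Trial: all 10 months of onsets up to month 12, plus months 15–18 and 21–24, so (10 + 6)/22 = 72.7%. Item 20: 10/22 = 45.5%.

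*Even onset, baseline reading (24 months, 2 to 26).* Trial: months 2–14, 17–20 and 23–26, so 18/24 = 75.0%. Item 20: 10/24 = 41.7%.

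*80% of onsets in months 2–12, the rest spread evenly to the end of follow-up.* Transplant reading: 0.8 + 0.2 × 6/12 = 90.0% v 80.0%. Baseline reading: 0.8 + 0.2 × 8/14 = 91.4% v 80.0%.

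**3. Apparent excess** = true incidence (the same in both groups) × difference in share caught.

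| Onset pattern | Reading | Difference in share | At 10% | At 20% |
|---|---|---|---|---|
| Even | Transplant | 27.3 points | 2.7 | 5.5 |
| Even | Baseline | 33.3 points | 3.3 | 6.7 |
| 80% by month 12 | Transplant | 10.0 points | 1.0 | 2.0 |
| 80% by month 12 | Baseline | 11.4 points | 1.1 | 2.3 |

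Episode length matters too. With even onset and 20% incidence, one-month episodes give 20% × (27.3% − 18.2%) = 1.8 points (transplant) or 20% × (29.2% − 16.7%) = 2.5 (baseline). Six-month episodes give 20% × (100% − 45.5%) = 10.9 or 20% × (100% − 41.7%) = 11.7.

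**4. Does a common window repair it?** Using only months 2 to 12 and titres in that window, the shares on the transplant reading are identical. On the baseline reading they are 40% v 40%, 70% v 70% and 90% v 100% for *d* = 1, 2 and 3. The ratio is therefore 0.9 to 1.0.

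**5. Against sampling error.** With illustrative counts of 11/55 and 10/50 (20% in each), the Newcombe 95% interval for the difference is −15.5 to +15.2 points.

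**The case against.** The strongest objection is that item 20 is not labelled as a control schedule. Item 13 says expressly that its approach was used for controls; item 20 does not. Its neighbours, items 21 and 22, read as instructions for trial patients, and the same-protocol statement in Study Design item 10 is about treatment. Item 20 and the visit table could be two accounts of the trial's own monitoring. This stands as a limit: the control schedule is inferred, and an absence of scheduled year-2 titres does not mean that no control had one. It does not remove the point. If item 20 does not govern controls, they have no stated BK schedule at all, and comparable testing still has to be shown from their records.

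Second, the plan is an unpowered pilot with descriptive comparisons, and the modelled bias is smaller than an interval of about ±15 points. That is fair and keeps the point modest, but imprecision does not correct a difference in detection that runs one way.

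Third, creatinine-prompted titres in controls would narrow the gap. That is true, and the documents do not allow it to be quantified.

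A reader might also infer three stronger things that the documents do not support:

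- **That trial patients are tested more often throughout.** The raw count of 7 v 4 suggests this, but year-1 testing is about equal.
- **That safety reporting as a whole is optional, or that data might be withheld.** The conditional wording covers only the overall adverse-event summary. Objectives 2b to 2q are stated without condition, serious adverse events are to be analysed, and publication is promised whatever the result.
- **That the by-group adverse-event table should be dropped** because no control source is described. That is missing detail which the analysts can supply.

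**Conclusion.** The point holds for 2m over 24 months. As written, the comparison has no window, and trial patients have scheduled titres in year 2 for which the documents show no counterpart in controls. The likely direction is an inflated BK incidence in the trial arm. The size cannot be fixed from the documents. Three-month episodes and 10% to 20% incidence give about 1 to 7 points, with the low end if most onsets fall in the first year and the high end if onsets are even over follow-up. None of these inputs is in the plan, and the result also rests on item 20 describing control testing. No single figure in that range should be read as an estimate.

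This is a minor design correction, worth making because it is nearly free. The optional adverse-event wording and the unstated control source are matters of reporting clarity only.

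**What to change.** Add to the Statistical Section, for 2m:

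- Compare BK infection over months 2 to 12 after transplant in both groups. Count every case in that window in both groups. Flag trial cases that arise before conversion but do not remove them: enrolment can be as late as month 6, and dropping those cases while keeping control cases from the same months would favour everolimus.
- Report the number of BK titres per patient in each group alongside the comparison.
- Describe trial-arm cases after month 12 separately, without a control figure. Extend the window only if control records show comparable year-2 testing.

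For 2n, list separately any case found only at the recommended 2-year biopsy.

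As a clarification, state that the adverse-event summary will be produced, and name the source and period of the control adverse-event data.

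The cost is a few sentences and the titre dates from the control record review that the secondary objectives already need. No visits or tests are added. The downside is that year-2 BK infection is described but not compared.

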The following data is in preparation for publication. Data was collected retrospectively for all patients transplanted between 3/14/2006 to 12/31/2007 at The University of Toledo Medical Center. There were *no exclusion criteria* other than limiting data to two transplant surgeons resulting in a study population of 143 patients. The first study group was given Prograf® (P) alone (47 patients) following transplantation, with the later group receiving Prograf® and myfortic® (P/M) (96 patients). Prograf® target level was 8 -12 ng/ml for both groups and myfortic® target dose was 720 mg PO bid adjusted for diarrhea and leukopenia. All patients were treated with Valcyte® and Bactrim® prophylaxis for 6-12 months. Review of the study populations showed no significance differences between the two immunosuppression groups for demographic details, death censored graft survival, patient survival, graft survival, rejection rate, one or two year creatinine level, severity of rejection (Banff score) or humoral rejection. Death censored graft survival rates after one year were 97.8% (P) and 89.4% (P/M). Two year death censored graft survival was 88.9% (P) and 85.6% (P/M). One year patient survival was 93.6% (P) vs 95.8% (P/M) and two year patient survival was 93.6% (P) vs 90.6% (P/M). Creatinine level at one year was 1.7±1.2 mg/dL (P) and 1.5±0.6 mg/dL (P/M) and at two years was 1.7±1.3 mg/dL (P) and 1.5±0.4 mg/dL (P/M). One year overall biopsy-proven rejection rates were 21.3% (P) vs 15.6% (P/M) and two year overall biopsy-proven rejection rates were 25.5% (P) vs 19.8% (P/M). Though not achieving statistical significance, our analysis demonstrated a trend toward differences in response to therapy based on ethnicity. At two years, rejection rates were 22.6% for Caucasians in both study groups, whereas in African-Americans, rejection rates were 45.5% (P) and 13% (P/M) (p=0.0789). While observing a 45% rejection rate in African-Americans treated with Prograf® in the absence of myfortic®, this increased rejection rate did not correspond to worsening two year graft survival that was 90.9%. Like the Miami experience, our data suggests caution with Campath® induction in African Americans, with two caveats: 1) our increased rejection rates were only seen in the absence of myfortic®; and 2) in the Miami study their results were limited by lower Prograf® bioavailability in African Americans.

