4. Resulted in persistent or significant disability/incapacity: *The event results in a substantial disruption of a person's ability to conduct normal life functions. The extent of the disability does not need to be permanent.*

5. Congenital anomaly / birth defect: *Any anatomical malformation or organ malfunction occurring in the offspring of a trial patient or subject.*

6. Other significant medical events: *Medical and scientific judgment should be exercised in deciding whether expedited reporting is appropriate in other situations, such as important medical events that may not be immediately life-threatening or result in death or hospitalization but may jeopardize the subject or may require intervention to prevent one of the other outcomes listed above. There may be other events judged to be medically serious or which are significant by specification in certain clinical trials.*

Suspected transmission of an infectious agent via a medicinal product should always be considered serious and assessed as medically significant in the absence of any other seriousness criteria. Cases of newly diagnosed cancer must be reported on a SAE form under 'other significant medical events' or hospitalization, death etc as appropriate. Cases of overdose which are life-threatening or result in death, hospitalization, significant disability or are considered medically significant should be reported on a SAE form. Overdose without clinical manifestation or leading to non-serious adverse events should not be reported on a SAE form.

Any AE, SAE or unanticipated problem occurring as a part of this trial that is considered related or possibly related to the patient's study treatment (immunosuppressive regimen) will also be reported to the University of Toledo Biomedical IRB Department for Human Research Protections on their corresponding internal adverse event reporting form within 7 days of the investigator becoming aware of the event as required by policy and in conformance with HHS and FDA regulations. Any pregnancies will be reported to Novartis within 24 hours of the investigator becoming aware of it.

The University of Toledo Biomedical IRB will have the authority to terminate IRB approval of research that is associated with unexpected serious harm to subjects.

Statistical Section:

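### The only numeric stopping limits are tied to the 10th enrolment, with no minimum follow-up, no time horizon and no statement whether they apply again

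*Combined protocol and SAP*

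**What the plan says.** The Statistical Section plans an early analysis: "we will analyze the data after we have enrolled 10 patients". The next sentence sets the limits: "If the study immunosuppression regimen has a > 40% Banff 2a rejection rate or greater than 20% patient death rate". Crossing either one ends the arm. No minimum follow-up, time horizon or denominator is given, and nothing says whether the limits are applied once or repeatedly.

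The same paragraph has the investigators and the transplant team meet "to review the results of this study on a quarterly basis" and says that serious adverse events "may serve as grounds for study discontinuation". Under AE Reporting, serious events go to the drug-safety team within 24 hours, and the IRB "will have the authority to terminate IRB approval of research". None of these carries a number.

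On accrual, Study Duration says "We plan to enroll 11 patients per year", and Study Design plans 55 patients over five years.

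The limit names Banff 2a. Items 14 to 16 of the Detailed Management Protocol speak instead of Banff 1, Banff 2 and humoral rejection.

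**The concern.** A pre-set limit should settle in advance what level of harm ends the trial. This one is triggered by enrolment, so its meaning depends on how long the first ten patients happen to have been followed. At the planned accrual that is short, and the last patient may only just have started. Rejection before entry cannot count, because patients must be rejection-free to enrol.

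Two things are at stake. Passing the look may be taken as evidence that rejection is below 40% and mortality below 20%, when it shows little more than the absence of gross early failure. And for the 45 patients enrolled afterwards, the reader cannot tell whether a numeric limit still applies or whether stopping rests on judgement alone.

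**Working it through.** The plan states no error rate or stopping probability for this rule, so there is no figure of its own to reproduce beyond accrual: 11 × 5 = 55.

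**Inputs.** Limits of 40% and 20% with n = 10 (Statistical Section); 11 patients per year (Study Duration). Assumptions: even accrual, conversion at enrolment, and limits read as 12-month risks after conversion.

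**Events needed.** More than 40% of 10 is 5 or more rejections. More than 20% of 10 is 3 or more deaths.

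**Follow-up on the day of the 10th enrolment.** Patient i has (10 − i) × 12/11 months: 9.8, 8.7, 7.6, 6.5, 5.5, 4.4, 3.3, 2.2, 1.1, 0. The mean is 4.9, and 4 of 10 have reached 6 months. With the analysis 3 months later, the mean is 7.9 and 7 of 10 have.

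**Stopping probability.** Under constant hazard and 12-month risk r, patient i has had the event with probability 1 − (1 − r)^(t/12), with t capped at 12. For the first patient at r = 40%: 1 − 0.6^(9.8/12) = 0.34. Summed over the ten, 1.8 rejections are expected against 5 needed; at r = 20%, 0.9 deaths against 3 needed. The exact tail of the sum of ten unequal Bernoulli variables gives:

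| Look | Timing of harm | True 40% rejection | True 20% death |
|---|---|---|---|
| Day of 10th enrolment | Constant hazard | 1.7% | 4.4% |
| Day of 10th enrolment | All within 3 months | 18–19% | 21% |
| 3 months later | Constant hazard | 11% | 14% |
| 3 months later | All within 3 months | 37% | 32% |

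The last row equals complete follow-up: P(X ≥ 5) for Bin(10, 0.4) is 0.367, and P(X ≥ 3) for Bin(10, 0.2) is 0.322.

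**Follow-up or sample size?** A rule of the form observed rate above limit stops less than half the time when the true rate sits exactly on the limit. With complete follow-up:

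| n | 40% rejection | 20% death |
|---|---|---|
| 10 | 37% | 32% |
| 20 | 40% | 37% |
| 55 | 44% | 42% |

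Going from 55 to 10 costs 7 to 10 points. Truncated follow-up on the day of the 10th enrolment takes 37% to between 1.7% and 19%, and 32% to between 4.4% and 21%. The cost of n = 10 shows above the limits: at 60% rejection with complete follow-up, 83% at n = 10 against 98% at n = 30.

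**Gross early failure.** On the day of the 10th enrolment, with all harm within 3 months, detection is 60–63% at 60% rejection and 80–83% at 70%. Under constant hazard it is 12% and 25%.

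**If the limits recur quarterly** as crude events over patients enrolled, simulation stops 74–100% of regimens at 40% rejection and 60–99.9% at 20% death, depending on event timing. False stops at a true 20% rejection run from about 2% to 24%. The width comes from the unstated horizon: second-year events count or not, as the reader chooses. The death range uses second-year hazard ratios taken from the centre's own series of 47 and 96 patients, which rest on a handful of deaths.

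**The case against.** The strongest reply is that the limits are not expressly confined to the 10-patient look. If they were meant to apply at every quarterly review, the rule is not weak, only incompletely worded. That stands, and it is why the low probabilities above must be tied to the one-time reading.

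Second, the analysis follows the 10th enrolment and need not fall on the same day. That also stands: a 3-month lag raises detection severalfold, although under constant hazard it remains at 11% and 14%.

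Third, this is an open-label, single-centre pilot that states it is not powered, with 24-hour reporting of serious events, quarterly review and IRB authority. A reader might infer that patients are left without protection after the tenth enrolment. The documents do not support that: oversight continues throughout. What is missing is a number attached to it. Being a pilot does not excuse leaving a mandatory limit undefined.

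A reader might also infer that ten patients is simply too few and that a larger interim sample would cure the problem. At the limits it would not; follow-up matters more there.

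**Conclusion.** The gap in the text is certain: no horizon, no minimum follow-up, no statement on recurrence, and a Banff category that does not match the management section. Its size depends on the reading. As a one-time look on the day of the 10th enrolment, the rule would seldom act on a regimen at its own limits: 1.7% and 4.4% under constant hazard, up to about 19% and 21% if harm is early. These figures assume even accrual at 11 per year and 12-month risks. The look can still catch gross early failure, so calling it useless would go too far. If the limits recur, the weakness largely disappears, but the rate still needs a horizon before anyone can compute it. This should be fixed, and wording is enough to do it.

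**What to change.** Keep the 40% and 20% limits and the look at 10. Add that the same limits are applied again at the quarterly reviews already planned, until the last patient completes, as a rate with a stated horizon. One example is a 12-month Kaplan-Meier estimate after conversion, starting when 10 patients were converted at least 12 months earlier, counting among the ten those who have since died or lost the graft. The horizon is the investigators' choice; another choice needs fresh probabilities.

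State the stopping probabilities. For the example, by simulation under constant hazard:

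| True 12-month rejection | Stopped | True 12-month death | Stopped |
|---|---|---|---|
| 15.6% | about 2% | 4.2% | about 2% |
| 20% | 5–6% | 6.4% | 5–6% |
| 40% | 77% | 20% | 77% |
| 50% | 98% | 30% | 98–99% |

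Say that the 77% reflects 21 repeated 12-month looks, of which the first gives about 0.47 for rejection and 0.44 for death. Mean enrolment at 40% rejection is about 32, against 54 if the look at 10 is the only one.

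The 15.6%, 4.2% (100 − 95.8) and 6.4% (100 − 93.6) are one-year figures from the centre's series in Background and Preliminary Data; 20% rejection is an assumption. That series had groups of 47 and 96, counted rejection of all grades from transplantation, and predates the steroid taper, so the false-stop rates are indicative only.

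Reconcile Banff 2a in the Statistical Section with the Banff 1, Banff 2 and humoral categories in the management items. Which grades count is for the investigators to decide.

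The cost is a protocol clarification and a short table at meetings already scheduled. The downside is a few percent of false stops, about 21 patients enrolled before the first 12-month look, and roughly 22–25% of regimens exactly at a limit still missed.
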